9.2.2 Sensitivity Analyses

Four sensitivity analyses will be conducted. The first two sensitivity analyses will repeat the primary analysis but will use the ITT and PP analysis sets.

The third sensitivity analysis will repeat the primary analysis using the mITT analysis set, but will apply a different method of imputation for missing data. The primary analysis treats all missing primary endpoints as having observed zero 2PN. There are instances, however, where the number

of 2PN for a subject with a missing primary endpoint could theoretically have been greater than zero. Such instances may include: withdrawal of consent, being lost to follow-up, having the study terminated by the sponsor, not attending key visits, due to the COVID-19 pandemic trial hold, or other reasons that would cause a subject with a potential non-zero 2PN count to have a missing value. The temporal nature of the above stated reasons for missing a non-zero 2PN count are such that a subject would need to have taken one or more doses of IMP and have a missing primary endpoint. A sensitivity analysis for the primary endpoint will be performed by using the multiple imputation approach which could impute a non-zero value for missing primary endpoints where it can be reasonably expected that the true value would have been non-zero. The following steps will be taken to implement the multiple imputation method:

- Imputation phase An ANOVA model with factors for treatment group, age strata, and center will be fitted to data from subjects in the mITT analysis set, less those subjects with missing primary endpoints. For each missing primary endpoint, a total of 1000 draws will be made from a normal distribution that is characterized by the estimated parameters from the fitted model and the factor values associated with the missing record. A total of 1000 complete datasets will be constructed.
- Analysis phase Each of the 1000 complete datasets will be analyzed using the ANOVA model described in Section 9.1.2.
- Pooling phase The estimated mean differences and standard errors from the analysis phase will be combined using Rubin's formula (Rubin 1987):

$$m_{MI} = \frac{1}{1000} \sum_{i=1}^{1000} m_i$$

$$se_{MI} = \sqrt{\frac{1}{1000} \sum_{i=1}^{1000} se_i^2 + \left(1 + \frac{1}{1000}\right) \left(\frac{1}{1000 - 1}\right) \sum_{i=1}^{1000} (m_i - m_{MI})^2}$$

where m_i and se_i are the estimated mean treatment difference and standard error for the treatment difference from the *i*th complete dataset and m_{MI} and se_{MI} are the pooled estimates. The mean difference in the number of 2PN between the MENOPUR liquid and the MENOPUR powder groups will be estimated as m_{MI} and the associated 95% confidence interval will be calculated as $m_{MI} \pm 1.96 * se_{MI}$.

The fourth sensitivity analysis will again repeat the primary endpoint analysis using the mITT analysis set but will instead use a 95.08% two-sided confidence interval to assess non-inferiority. This sensitivity analysis assesses the impact of any Type I error inflation incurred due to performing a blinded sample size recalculation during a non-inferiority study. See Appendix 1 for more details.

Ferring Pharmaceuticals

Furthermore, the number of fertilized oocytes will be summarized for several subgroups:

- By reason for infertility
- By center
- By number of oocytes retrieved (<4, 4-7, 8-14, 15-19, and ≥20)
- By AMH level on stimulation day 1 (<7.5, 7.5-<15, 15-<25, ≥25 pmol/L; ≤ median, > median)

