3.2 Sample Size

The present trial is a pharmacodynamic comparison of a marketed product to a new formulation of the same. With 188 subjects per treatment group, the trial has at least 85% power to demonstrate the non-inferiority of MENOPUR liquid to MENOPUR powder in the number of fertilized oocytes at the 1-sided significance level of 0.025. This is based on the results for MENOPUR powder from the COMBINE trial (data on file) conducted in a similar setting (GnRH agonist protocol, MENOPUR starting dose of 225 IU for the first five days, insemination by ICSI etc.) and in a similar population (infertile women between 18 and 42 years). The mean (SD) of the number of fertilized oocytes were 7.88 (5.15) with similar results in the two age groups (7.92 in the <35 years age group vs. 7.80 in

the \geq 35 years age group). The non-inferiority margin of -1.60 will retain 80% of the expected comparator effect.

After adjusting for 5% missing data, approximately 400 subjects will be randomized (1:1) into this trial, stratified by trial site and age (<35 years and \geq 35 years).

A blinded sample size reassessment will be done when data on the primary endpoint are available for 70% of the planned subjects or when 300 subjects are randomized, whichever comes first. The sample size reassessment will be done without breaking the blind and without inflating the type I error of the trial, in line with current regulatory guidelines. The expected maximum number of subjects to be randomized is 500 (250 subjects per treatment group), corresponding to a blinded one-sample (both groups pooled) standard deviation estimate of 5.8 and 85% power.

4 Subject Disposition

All subjects screened will be accounted for. The number of subjects screened but not randomized to treatment will be presented with the reason for screen failure.

Subject disposition with respect to each analysis set will be tabulated. The number of subjects in the intention-to-treat (ITT) analysis set will be used as the denominator when calculating percentages. Randomized subjects, randomized subjects treated with investigational medicinal product (IMP; MENOPUR liquid including Placebo to MENOPUR powder or MENOPUR powder including Placebo to MENOPUR liquid), and randomized subjects prematurely discontinued from the trial will be summarized. Randomized subjects prematurely discontinued from the trial will have the reason for premature discontinuation summarized.

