Using the methods described in Appendix 1 of Friede and Kieser (2003), a simulation study was performed. The simulation study assessed the potential Type I error of the present trial given the design considerations for the sample size recalculation (See Section 3.2). The 'true' pooled standard deviation was set to range from 3.0 to 15.0 using increments of 0.1. For each increment, 10,000,000 simulations were performed. Based upon the design considerations of the present trial, the minimum sample size was set to 400, the maximum sample size was set to 500, and the sample size recruited at the time of the sample size recalculation was set to 280. Likewise, when recalculating the sample size during each simulation rep, an alternative treatment difference of 0 was assumed, the non-inferiority margin was set to -1.6, a two-sided alpha of 0.05 was used, and the power was set to 85%.

The results of the simulation can be seen in Figure 0-1 below. For true pooled standard deviations that are less than 5 and greater than 6, the Type I error is well controlled. For true pooled standard deviations between 5 and 6, there is a small amount of Type I error inflation. The maximum Type I error observed was 0.0253705, which occurred at a true pooled standard deviation of 5.6.

Figure 0-1: Actual Type I error of the 000303 trial given the true pooled standard deviation.

One conservative method for controlling the maximum Type I error inflation was illustrated by Friede and Stammer (2010). An iterative procedure is performed, adjusting alpha until the maximum observed Type I error is within a certain distance, epsilon, of the predefined desirable level of Type I error. This method was applied to the present trial by setting epsilon equal to 0.0001 (i.e.; a maximum Type I error no greater than 0.0251).

The results of applying the procedure can be seen in Figure 0-2 below. When adjusting the onesided Type I error from 0.025 to 0.0246 (or, equivalently, the two-sided Type I error from 0.05 to 0.0492), the maximum observed Type I error is within 0.0001 of the pre-specified Type I error of 0.025. The maximum observed Type I error was 0.0250291 and again occurred at a standard deviation of 5.6.

Figure 0-2: Adjusted Type I error after applying an alpha correction.

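### The multiple-imputation sensitivity analysis draws every imputation at one fixed set of fitted parameters and then pools with Rubin's formula, so its standard error is slightly too small (about 0.5% at the planned 5% missing).

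*SAP*

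**What the plan says.** The primary analysis (SAP 9.2.1) sets every missing count of fertilized oocytes to zero. SAP 9.2.2 adds four sensitivity analyses. The ITT, per-protocol and 95.08%-interval analyses all repeat the primary analysis, so they keep the zero rule. Only the third analysis replaces it, with multiple imputation in three phases:

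- **Imputation.** One ANOVA with treatment, age strata and center is fitted to the mITT subjects whose endpoint is observed. For each missing endpoint, 1000 "draws will be made from a normal distribution that is characterized by the estimated parameters from the fitted model" and from the subject's own factor values.
- **Analysis.** Each of the 1000 completed datasets is analysed with the ANOVA of SAP 9.1.2, in which center is a fixed effect.
- **Pooling.** "The estimated mean differences and standard errors from the analysis phase will be combined using Rubin's formula". The total variance is the mean squared standard error plus (1 + 1/1000) times the between-dataset variance, and the interval is the pooled estimate ± 1.96 standard errors.

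Nothing in SAP 9.2.2 or elsewhere redraws the model parameters from one dataset to the next. The SAP's version history records that V1.0 imputed from a negative binomial model and that V2.0 changed this to the ANOVA so that the imputation and analysis models agree.

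**The concern.** Rubin's total variance is meant to cover two sources of uncertainty about a missing value: the scatter of individuals around the model, and the uncertainty of the model itself. The second enters only if the imputation parameters vary between datasets, for example through posterior draws or bootstrap refits. When all 1000 datasets share one set of estimates, the between-dataset variance holds individual scatter only, and the pooled standard error is too small. Raising the number of imputations does not help, because the missing component is absent from every dataset.

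Two things make this worth correcting. In a non-inferiority comparison, an interval that is too narrow errs in favour of the new formulation. And this analysis is the plan's only check on the zero rule for missing counts.

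**Working it through.** **Inputs.** SAP 3.2 gives SD 5.15, margin 1.60, testing "at the 1-sided significance level of 0.025", and "After adjusting for 5% missing data, approximately 400 subjects will be randomized (1:1) into this trial". Appendix 1 of the SAP states that "an alternative treatment difference of 0 was assumed". The protocol synopsis allows up to 25 centers. The documents do not give the fraction of endpoints actually missing, so 5% is the planning allowance and 10% and 20% are assumptions.

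**Step 1: the plan's own figure.** n per arm = 2(1.960 + 1.036)² × 5.15² / 1.60² = 2 × 8.978 × 26.52 / 2.56 = 186.0, so 187. The SAP states "With 188 subjects per treatment group, the trial has at least 85% power"; power at 188 is 85.4%. Then 376/0.95 = 396, stated as about 400. The planning figures reproduce. The SAP gives no figure for the imputation standard error.

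**Step 2: simplest case, two arms and no covariates.** With n per arm and a fraction f missing, per arm:

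- within-dataset variance W = s²/n
- between-dataset variance with fixed parameters B = f·s²/n
- pooled variance T = (1 + f)s²/n
- true variance of the estimate V = s²/[n(1 − f)]
- T/V = (1 + f)(1 − f) = 1 − f²

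The shortfall in the standard error, 1 − √(1 − f²), is 0.13%, 0.50% and 2.02% at f = 5%, 10% and 20%. This leaves out the center effects in the SAP model, so it is a low estimate.

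**Step 3: the SAP's model with fixed centers.** Let X be the full design matrix with p = 27 columns (intercept, treatment, age strata, 24 center indicators), Xo its observed rows, Xm its missing rows and A = (X′X)⁻¹. Subscript t marks the treatment term. With many imputations the pooled estimate equals the observed-case estimate, so:

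- V = σ²[(Xo′Xo)⁻¹]ₜₜ
- B = σ²[A Xm′Xm A]ₜₜ
- W = σ²Aₜₜ × [n − p − tr(Xm A Xm′)]/(n − p)
- T = W + B (the extra factor of 1/1000 on B is negligible)

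With n = 400, σ = 5.15, 25 centers of 16 subjects, age strata assigned at random and values missing at random, averaged over 1500 random layouts:

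| Missing | W | B | T | V | √T | √V | SE too small by | Lower limit too high by 1.96(√V − √T) |
|---|---|---|---|---|---|---|---|---|
| 5% | 0.2650 | 0.0133 | 0.2783 | 0.2810 | 0.5275 | 0.5301 | 0.5% | 0.005 |
| 10% | 0.2640 | 0.0266 | 0.2906 | 0.2978 | 0.5391 | 0.5457 | 1.2% | 0.013 |
| 20% | 0.2620 | 0.0532 | 0.3152 | 0.3382 | 0.5614 | 0.5815 | 3.5% | 0.039 |

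The last column is in oocytes.

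**Step 4: simulation against proper imputation.** The full procedure was simulated under the same layout (1500 trials, 300 imputations each), with fixed parameters and with parameter draws. Mean pooled standard errors were 0.5266 against 0.5299 (0.6%), 0.5379 against 0.5460 (1.5%) and 0.5623 against 0.5820 (3.4%) at 5%, 10% and 20% missing. This agrees with Step 3. The simulated rejection rates were too noisy to use.

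**The case against.** The strongest reply is that nothing turns on this. The non-inferiority claim rests on the mITT analysis with missing counts set to zero, and the SAP attaches no success rule to the imputation analysis. A reader might infer that the trial can pass its margin more easily because of this step; the documents do not support that. At the planned 5% missing, a conclusion would differ only if the lower limit fell within about 0.005 of -1.60. As a one-sided error rate, the shortfall corresponds to Φ(−1.96 × 0.995) ≈ 0.0255. SAP Appendix 1 reports a maximum of 0.02537 from the blinded sample-size review and treats it as negligible for the primary analysis. All of this stands. It limits the size of the point but does not make the variance formula right. The sponsor still added a sensitivity analysis for an inflation of similar size.

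A reader might also infer that the COVID-19 halt pushes missingness well above 5%. The documents do not show that. Protocol amendment 04 kept randomized subjects in the trial per protocol, and SAP section 4 treats subjects still in screening as screen failures, who cannot be in the mITT set. SAP 9.2.2 does list the halt among possible reasons for a missing endpoint, so a larger fraction is not excluded, but 10% and 20% remain assumptions. The same section speaks of imputing where a non-zero count could be expected and then of imputing every missing endpoint, so the number imputed is not settled either.

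Finally, a reader might see a second defect in the impossible values. At mean 7.88 and SD 5.15, 6.3% of normal draws are negative, and draws are not whole numbers. This does not hold as a fault. V2.0 chose the ANOVA deliberately to match the analysis model, and under that linear model negative draws do not bias the mean difference. Truncating them at zero would raise the imputed means.

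**Conclusion.** The point holds as a small technical error. As written, the third sensitivity analysis leaves parameter uncertainty out of its pooled variance, and its 95% interval is too narrow. The standard error is about 0.5% too small at the planned 5% missing, rising to about 1.2% and 3.5% if 10% or 20% were missing. These figures assume 400 subjects, 25 equal centers, SD 5.15 and values missing at random. Fewer centers would bring them closer to the 0.13%, 0.50% and 2.02% of the case without covariates. The primary analysis and the other three sensitivity analyses are untouched.

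**What to change.** Replace the draw step in SAP 9.2.2 with:

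*For each of the 1000 imputations, the residual variance and regression coefficients of the ANOVA model will first be drawn from their posterior distribution (PROC MI, MONOTONE REG), and the missing values will then be drawn from the normal distribution with those parameters.*

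The analysis and pooling phases stay as they are. Negative and non-integer draws can remain, for compatibility with the ANOVA. Refitting on bootstrap samples would also carry the parameter uncertainty, but the SAP should name one method. The cost is one sentence: the named procedure makes the parameter draw by default, no further data are needed, and the primary analysis does not change.

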9.3 Secondary Efficacy Endpoints

Secondary efficacy endpoints will be analyzed based on the mITT analysis set and summarized based on both the mITT and PP analysis sets. For several endpoints, summaries consisting of subgroups of the mITT analysis set will be presented. Descriptive summaries will be tabulated as described in Section 1.2.1.

9.3.1 Positive βhCG Rate

The positive β hCG rate will be presented by treatment group and analyzed using the method described for secondary pregnancy endpoints in Section 9.1.2. Subjects who do not have a confirmed positive β hCG test will be counted as not having positive β hCG unless a positive clinical or ongoing pregnancy outcome is observed later. For example, if the outcome β hCG is missing, but the clinical pregnancy outcome is 'positive' then β hCG will be imputed as 'positive'.

9.3.2 Clinical Pregnancy Rate

The clinical pregnancy rate will be presented by treatment group and analyzed using the method described for secondary pregnancy endpoints in Section 9.1.2. Subjects who do not have at least 1 intrauterine gestational sac, confirmed by TVUS, with a fetal heart beat at 5-6 weeks after blastocyst transfer will be counted as not having clinical pregnancy unless a positive ongoing pregnancy outcome is observed later. For example, if the clinical pregnancy assessment is missing, but the ongoing pregnancy outcome is 'positive' then clinical pregnancy will be imputed as 'positive'.

9.3.3 Ongoing Pregnancy Rate

The ongoing pregnancy rate will be presented by treatment group and analyzed using the method described for secondary pregnancy endpoints in Section 9.1.2.

9.3.4 Number and Size of Follicles During Stimulation

The follicle cohort on stimulation day 6 and the last day of stimulation will be summarized by treatment on the follicle level (number of follicles ≤ 9 mm, 10-11 mm, 12-14 mm, 15-16 mm, and ≥ 17 mm) and the subject level (largest follicle size and average number of follicles ≥ 17 mm, ≥ 15

mm, and ≥ 12 mm). The subject level parameters will be analyzed as described in Section 9.1.2 for the primary endpoint.

9.3.5 Levels of Endocrine Parameters

The levels of endocrine parameters will be presented by treatment group for both the scheduled visit and the change from baseline for post-baseline visits. Baseline values for endocrine parameters are calculated as defined in Section 1.1.1. Values below the lower limit of quantification (LLOQ) will be included as LLOQ/2. Values above the upper limit of quantification (ULOQ) will be included as ULOQ.

The following list describes which post-baseline visits (and, consequently, change from baseline calculations) are summarized for each of the endocrine parameters.

- AMH: End-of-stimulation and end-of-trial.
- FSH: Stimulation day 6, end-of-stimulation, and oocyte retrieval.
- hCG, LH, Estradiol, and Progesterone: Stimulation day 6 and end-of-stimulation.

For each parameter the change from baseline will be compared between treatment groups using a log-normal model. In this model, the follow-up measurement will be the dependent variable and the linear predictors will include treatment, age strata, and center as factors as well as the baseline measurement (log-transformed) as a covariate. Inferential results will be presented as described in Section 1.2.2.

9.3.6 Number of Oocytes Retrieved

The number of oocytes retrieved will be presented by descriptive statistics by treatment group and analyzed as described in Section 9.1.2 for the primary endpoint. Furthermore, a frequency table with subjects grouped according to their number of oocytes retrieved will be prepared using these categories: ≤ 3 , 4-7, 8-14, 15-19, and ≥ 20 oocytes. Subjects without oocyte retrieval will be imputed to have 0 oocytes retrieved. For example, if the cycle is cancelled due to poor ovarian response, the number of oocytes retrieved is imputed as 0. Additional subgroup summaries of the number and distribution of oocytes retrieved for subjects with oocytes retrieved will also be presented.

9.3.7 Number of Metaphase II Oocytes

Oocytes will have their maturity stage assessed prior to insemination. Maturity stage will be categorized as germinal vesicle, metaphase I, metaphase II, degenerated, or other. For subjects that have oocytes retrieved, but are missing maturity stage information, the maturity stage of their oocytes will be regarded as unknown (i.e.; not metaphase II).

The number and distribution (\leq 3, 4-6, 7-12, 13-17, and \geq 18) of MII oocytes will be presented by descriptive statistics by treatment group. Furthermore, the number of inseminated oocytes, the sperm source, and the sperm type will also be presented by descriptive statistics by treatment group.

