6.3 Oocyte Retrieval

Oocyte retrieval must take place 36±2 hours after hCG administration. All oocytes from follicles with an estimated diameter ≥12 mm should be retrieved. Oocytes will be inseminated using partner or donor sperm by ICSI 4±2 hours after retrieval.

Below are listed the procedures related to the subjects attending the oocyte retrieval visit, while procedures related to the oocytes are described in section 6.3.1.

The following must take place at the oocyte retrieval visit:

- Oocyte retrieval
- Progesterone (ENDOMETRIN) for luteal phase support dispensed [note: progesterone must be started the day after oocyte retrieval and continued up to menses, negative βhCG, pregnancy loss or for a maximum of 10 weeks total if pregnancy is confirmed]
- Blood collection for central laboratory analysis of endocrine parameters (FSH only)
- Recording of use of any concomitant medication
- Recording of adverse events

For subjects with oocytes retrieved following hCG administration, the next visit is the transfer visit 5 days after oocyte retrieval.

For subjects with no oocytes retrieved, the next visit is the first post-dosing anti-MENOPUR antibody assessment visit (section 6.4.2).

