2.2 Endpoints

Primary Endpoint

• Number of fertilized (2 pronuclei [2PN]) oocytes at 19±2 hours after insemination.

Secondary Endpoints

- Positive βhCG rate (positive βhCG test 10-14 days after blastocyst transfer).
- Clinical pregnancy rate (transvaginal ultrasound showing at least 1 intrauterine gestational sac with fetal heart beat 5-6 weeks after blastocyst transfer).
- Ongoing pregnancy rate (at least one intrauterine viable fetus 8-9 weeks after blastocyst transfer).

Ferring Pharmaceuticals

- Early pregnancy loss (defined as a positive βhCG test but no ongoing pregnancy at 8-9 weeks after blastocyst transfer).
- Follicular development as assessed by transvaginal ultrasound on stimulation day 6 and last day of stimulation.
- Endocrine profile:
 - Serum follicle-stimulating hormone (FSH) on day 6, last day of stimulation and at oocyte retrieval, and corresponding population pharmacokinetics (PK) analysis.
 - Serum Anti-Müllerian hormone (AMH) on last day of stimulation and at end-of-trial.
 - Human chorionic gonadotropin (hCG) and luteinizing hormone (LH) on day 6 and last day of stimulation.
 - Estradiol (E2) and progesterone (P4) on day 6 and last day of stimulation.
- Number of oocytes retrieved, number of metaphase II oocytes, fertilization rate, and number and quality of blastocysts 5 days after oocyte retrieval.
- Total gonadotropin dose and number of stimulation days.
- Frequency of OHSS (early OHSS if the onset is ≤9 days after triggering of final follicular maturation and late OHSS if the onset is >9 days after triggering of final follicular maturation).
- Frequency and intensity of adverse events.
- Changes in circulating levels of clinical chemistry and hematology parameters and proportion of subjects with markedly abnormal changes.
- Frequency and intensity of injection site reactions (redness, pain, itching, swelling and bruising) assessed by the subject during the stimulation period.
- Frequency of treatment-induced anti-MENOPUR antibodies, overall as well as with neutralizing capacity.
- Technical malfunctions of the pen.

Post-trial Endpoints

- Live birth rate.
- Late pregnancy loss rate (defined as an ongoing pregnancy but no live birth).

• Neonatal health including SAEs at birth, and SAEs at 4 weeks and minimum 6 months after birth.

3 Trial design

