9.3.8 Fertilization Rate

For subjects with >0 oocytes retrieved, the rate of fertilized oocytes to oocytes retrieved will be presented by descriptive statistics by treatment group. Furthermore, for subjects with >0 metaphase II oocytes, the rate of fertilized oocytes to metaphase II oocytes will be presented by descriptive statistics by treatment group. Fertilization rates will be summarized based on the subset of the mITT analysis set.

9.3.9 Number and Quality of Blastocysts on Day 5

The embryos on Day 5 after oocyte retrieval will be summarized on both the embryo level and on the subject level.

Embryo Level

At the embryo level all embryos evaluated will be included in the tables when reporting embryo stage, destiny, and grading. Frequency tables will be produced for the embryo stage, destiny at day 5, blastocyst expansion and hatching status, blastocyst inner cell mass grading, and trophectoderm grading.

Subject Level

At the subject level the following variables will be derived for all subjects in the analysis set. For any subject that did not have a blastocyst, did not have oocyte retrieval, or otherwise had a missing subject-level endpoint, a value of 'NO' or 0 will be imputed, as appropriate.

- At least one blastocyst available
- At least one good-quality blastocyst available
- Number of blastocysts
- Number of good quality blastocysts
- Number of blastocysts transferred

Among the above variables, the number of blastocysts and the number of good quality blastocysts will be analyzed as described in Section 9.1.2 for the primary endpoint. The dichotomous variables of having at least one blastocyst available and of having at least one good quality blastocyst available will be analyzed as described in Section 9.1.2 for secondary pregnancy endpoints. No analysis will be performed for the remaining variables in this section.

At the subject level the following variables will be derived for mITT analysis set subjects that had oocytes retrieved:

• Rate of blastocysts to oocytes retrieved

• Rate of good-quality blastocysts to oocytes retrieved

At the subject level the following variables will be derived for mITT analysis set subjects that had at least one fertilized oocyte:

- Rate of blastocysts to fertilized oocytes
- Rate of good quality blastocysts to fertilized oocytes

10 Safety

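### SAP 9.3.7 scores a woman with no maturity record as having zero metaphase II oocytes, even when fertilized oocytes were recorded for her

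*SAP*

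**What the plan says.** The MII count is a named secondary endpoint. SAP section 2.2 lists "Number of oocytes retrieved, number of metaphase II oocytes, fertilization rate" together, and the protocol's section 2.2 does the same.

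SAP section 9.3.7 sets the timing: "Oocytes will have their maturity stage assessed prior to insemination". For women with oocytes retrieved but no maturity data it then gives the rule: "missing maturity stage information, the maturity stage of their oocytes will be regarded as unknown (i.e.; not metaphase II". The section makes no exception for oocytes later seen to be fertilized. The number and distribution "of MII oocytes will be presented by descriptive statistics by treatment group", with 3 or fewer as the lowest category. The same section adds that "the number of inseminated oocytes, the sperm source, and the sperm type will also be presented", but it does not use the number inseminated to check or correct the MII count.

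SAP section 9.3.8 uses MII as a denominator: "for subjects with >0 metaphase II oocytes, the rate of fertilized oocytes to metaphase II oocytes will be presented". This is in addition to the rate over oocytes retrieved, which is how protocol sections 7.2.8 and 9.6.3 define fertilization rate.

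Pronuclei are counted separately, 19±2 hours after insemination (protocol sections 6.3.1 and 7.2.8). On insemination itself, protocol section 6.3 says: "Oocytes will be inseminated using partner or donor sperm by ICSI 4±2 hours after retrieval". It does not say that only MII oocytes are injected.

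**The concern.** The rule turns a gap in the record into a negative finding, although the trial may hold evidence against it. The 2PN count is the primary endpoint and is recorded after the maturity step. By forming a rate of 2PN over MII, the SAP itself treats fertilized oocytes as a subset of MII oocytes. A woman with MII = 0 and several 2PN oocytes breaks that relation.

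Two outputs are affected. The MII mean and frequency table take in a zero that is too low, and the 2PN/MII rate loses the woman with no note that she was dropped. What is at stake is the accuracy and internal consistency of a secondary endpoint, not the trial's main conclusion.

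**Working it through.** **1. The plan's own figure.** The documents state no figure for MII or for missing maturity. The nearest stated figure is the primary sample size (protocol section 9.1, SAP section 3.2): margin 1.60, SD 5.15, one-sided alpha 0.025, power 85%, true difference 0 (SAP Appendix 1).

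n per arm = 2 × (1.960 + 1.036)² × 5.15² / 1.60² = 186.04, rounded up to 187. The plan states 188, at which power is 85.4% (normal) or 85.2% (noncentral t). The figure reproduces, and MII does not enter it.

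**2. The rule applied to one woman.** Illustrative values, not from the documents: 10 oocytes retrieved, 8 truly MII, 7 scored 2PN.

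| Maturity record | MII as scored | 2PN/MII |
|---|---|---|
| Complete | 8 | 7/8 = 87.5% |
| None | 0 | not computed; she leaves the rate |
| Partial, 4 recorded as MII | 4 | 7/4 = 175% |

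The second row follows from the text on any reading. The third arises only if the rule is applied oocyte by oocyte.

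**3. Effect on an arm mean.** Let f be the share of women in an arm with no maturity record. Each is scored 0, when her MII count should be at least her 2PN count. With the planning mean of 7.88 2PN (protocol section 9.1) as the floor:

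minimum shortfall = f × 7.88

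| f (assumed) | Women of 200 | Minimum shortfall in mean MII |
|---|---|---|
| 0.5% | 1 | 0.04 |
| 1% | 2 | 0.08 |
| 2% | 4 | 0.16 |
| 5% | 10 | 0.39 |
| 10% | 20 | 0.79 |

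**4. Effect on the difference between arms.** The difference shifts by about (f₁ − f₂) × 7.88. With equal shares this is about zero. As a purely hypothetical imbalance, 5% versus 2% gives 0.03 × 7.88 = 0.24. For scale, with the 2PN SD as a stand-in for the MII SD, the standard error of a difference at 200 per arm is 5.15 × √(2/200) = 0.515, so 0.24 is about 0.46 of a standard error.

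**5. The SAP's handling of similar gaps.** In sections 9.3.1 and 9.3.2, a missing βhCG or clinical pregnancy result is set to positive when a later pregnancy assessment shows it must have been positive. Section 9.3.7 has no such clause, although fertilization follows maturity in the same way.

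**The case against.** The strongest reply is that this is a rare-case rule on a descriptive summary. Maturity assessment is a scheduled step before every ICSI (protocol Table 6-2 and section 7.2.7), so gaps should be few. Section 9.3.7 specifies no model, whereas sections 9.3.6 and 9.3.9 expressly send oocytes retrieved and blastocyst counts to the model in section 9.1.2. That section's general wording on continuous secondary endpoints leaves some doubt whether MII is also modelled. Individual efficacy data are listed (SAP section 1.2.3), so an odd record could be seen. All of this stands and limits the weight of the point.

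It can also be said that the SAP generally counts unconfirmed outcomes as zero or negative. That is true for 2PN, oocytes retrieved and blastocysts. For βhCG and clinical pregnancy, however, the convention yields to later evidence, and that is the part missing here.

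The rule's opening refers to subjects lacking maturity information, which reads most naturally as a condition on the woman. On that reading the result is always zero, she leaves the 2PN/MII rate, and the rule cannot push the rate above 100%. The objection is fair; the wording does not settle partial records.

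Two stronger readings are tempting and not supported. A reader might infer that the rule creates a spurious treatment difference. The documents show no mechanism for one: embryologists are blinded, the rule is the same in both arms, and randomization is stratified by site. A reader might also infer that the number inseminated proves how many oocytes were MII. The documents never restrict injection to MII oocytes, so ICSI alone proves nothing about maturity.

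**Conclusion.** The point holds and is minor. Section 9.3.7 assigns MII = 0 to a woman with no maturity record whatever her 2PN count, and nothing elsewhere in either document corrects it. Arm means of MII are too low by at least about 0.08 oocytes per 1% of women affected, and those women drop out of the 2PN/MII rate.

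The size rests on three assumptions. The share of women affected is not given, and the 0.5% to 10% range is illustrative. Affected women are taken to have, on average, the planning mean of 7.88 2PN oocytes. Every 2PN oocyte is taken to have been MII, as the SAP's own rate implies.

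Rates above 100% are conditional on the rule covering partial records. It would be wrong to read the point as a threat to the non-inferiority test, the sample size or the fertilization rate over oocytes retrieved; none of them uses the MII count.

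**What to change.** Amend the rule in SAP section 9.3.7 along these lines:

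- Where maturity is missing, set the woman's MII count to no less than her recorded 2PN count. Use the observed count, not the zero imputed for the primary analysis.
- If there is no 2PN evidence, set her MII count to missing rather than zero.
- Show the number of such women in each arm.
- State whether partly missing maturity records are covered.
- State in section 9.3.8 how these women enter the 2PN/MII rate. A woman whose MII count is set equal to her 2PN count would contribute exactly 100%, so leaving her out and showing the count is one clear option.
- Do not infer MII from ICSI alone.

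The cost is a few sentences in the SAP and one changed derivation. A floor for each woman needs only her 2PN count, which is already collected as the primary endpoint. No sample size, alpha or primary analysis changes.
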